5.5.3. Vital Signs

Baseline values and change from baseline values will be summarized with descriptive statistics by hepatic group and for each nominal visit over time.

The number and percent of patients in each of the following minimum and maximum blood pressure, body weight and pulse rate categories will be presented,

| Vital Sign | Category |
|----------------|---|
| Blood Pressure | Maximum Change from baseline (increase) in SBP of ≥40 mmHg |
| | Maximum Change from baseline (decrease) in SBP of ≥40 mmHg |
| | Maximum Change from baseline (increase) in SBP of ≥60 mmHg |
| | Maximum Change from baseline (decrease) in SBP of ≥60 mmHg |
| | Maximum Change from baseline in DBP (increase) of ≥20 mmHg |
| | Maximum Change from baseline in DBP (decrease) of ≥20 mmHg |
| | Maximum Change from baseline in DBP (increase) of ≥40 mmHg |
| | Maximum Change from baseline in DBP (decrease) of ≥40 mmHg |
| Body Weight | Maximum change from baseline body weight (increase) $\geq 20\%$ |
| | Maximum change from baseline body weight (decrease) $\geq 10\%$ |
| Pulse Rate | Minimum Pulse Rate <50 bpm |
| | Maximum Pulse Rate >120 bpm |

5.5.4. Electrocardiogram

A triplicate 12-lead will be used for all ECG assessments.

All patients require a triplicate ECG measurement at screening and at each scheduled time point during treatment. A mean score is calculated for the replicate measurements having the same nominal visit, and will be reported.

QT, RR, HR, PR, QRS, QTcF (Fridericia correction), and QTcB (Bazett's correction) data will be provided by sites on the ECG page of the CRF.

The analysis of ECG results will be provided for safety analysis set patients with baseline and on-treatment ECG data by hepatic group and for each nominal visit over time. ECG measurements collected closest prior to the first dose of study drug will be used as the baseline ECG for analysis.

ECG measurements (an average of the triplicate measurements) will be used for the statistical analysis and all data presentations. Any data obtained from ECGs repeated for safety reasons after the nominal time points will not be averaged along with the preceding triplicates. Interval measurements from repeated ECGs will be included in the outlier analysis as individual values obtained at unscheduled time points.

Descriptive statistics (n, mean, median, standard deviation, minimum, and maximum) will be used to summarize the absolute value and changes from baseline in QT, QTcF, QTcB, HR, RR, PR, QRS after treatment by hepatic group and nominal visit.

The number (%) of subjects with maximum post dose QTc values and maximum increases from baseline in the following categories will be tabulated:

| Absolute Value (msec) | ≥450 -<480 |
|------------------------|------------|
| | ≥480 -<500 |
| | ≥500 |
| Absolute Change (msec) | 30-<60 |
| | ≥60 |

The number (%) of subjects with maximum post-dose PR interval values and maximum increases from baseline in the following categories will be tabulated:

| Absolute Value (msec) | <160 |
|-------------------------------|-------------|
| | ≥160 - <180 |
| | ≥180 - <200 |
| | ≥200 - <220 |
| | ≥220 - <240 |
| | ≥240 - <260 |
| | ≥260 |
| Absolute Change (msec) | 40-<60 |
| | ≥60-<80 |
| | ≥80 |
| Relative Change from baseline | >25% |

Shift tables will be provided for baseline vs worst on study PR using the categories in the above table. The effect of drug concentrations on QTc change (and PR interval) from baseline will be explored graphically.

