- 14. **12-Lead ECG**: Triplicate ECG will be performed at screening, times 0 (predose) 1, 2, 4, 10 and 24 hours post dose on Cycle 1 Day 1 and Cycle 2 Day 1, predose on days 8 and 15 in cycle 1, and at the end of treatment. At each time point, 3 consecutive 12-lead ECGs are to be performed approximately 2 minutes apart. The ECG must occur prior to any blood sample collections or venipuncturing or collection of vital signs. All ECGs scheduled at 0 hours must be collected prior to dosing. All efforts should be made to ensure the ECG collections completed within 15 minutes prior to the PK collection if they are planned at the same time. Additional ECGs may be collected as clinically indicated. Single reading ECG will be collected pre-dose on Day 1 of Cycle 3 and every cycle thereafter.
- 15. LVEF Assessment: Echocardiogram or MUGA to be performed at Screening, at pre-dose (0 hour) on Cycle 1 Day 1 (not required if screening LVEF was obtained within 7 days prior to Cycle 1 Day 1) and on Day 1 of every other cycle thereafter, and at the EOT visit. The same method should be used at each time point.
- 16. Enrollment: Enrollment number and treatment group allocation assigned by Pfizer Inc based on AST and total bilirubin values.
- 17. **Tumor Assessments**: Tumor assessments will include all known or suspected disease sites. Imaging may include CT or MRI scans of chest, abdomen, and pelvis. Brain scans and bone scans will be performed at screening if disease is suspected and on study as appropriate to follow disease. The Investigator evaluation will be used for response analysis according to RECIST v1.1. Tumor assessment should be repeated at the end of treatment visit if more than 6 weeks have passed since the last evaluation.

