## 7.1.6. (12-Lead) Electrocardiogram

A triplicate 12-lead (with a 10-second rhythm strip) tracing at supine position will be used for all ECG assessments.

All patients require a triplicate ECG measurement at screening. On treatment ECGs will be performed as outlined in the Schedule of Activity (SOA) table. At each time point requiring triplicate ECGs, 3 consecutive 12 lead ECGs will be performed approximately 2 minutes apart to determine mean QTc (average of triplicates). When they coincide with blood sample draws for PK, the ECG assessment should be performed within 15 minutes prior to a PK blood sample collection, such that the PK blood sample is collected at the planned nominal time.

Clinically significant findings seen on subsequent ECGs should be recorded as adverse events. In case of QTc >500 msec (ie, CTCAE Grade >2), ECG must be reviewed by qualified personnel at the site as soon as the finding is made, including verifying that the machine reading is accurate and that the Fridericia correction formula is applied. If the manual reading verifies a rate corrected QTc of >500 msec, repeat ECG should be immediately performed at least two times approximately 2 to 4 minutes apart.

An electronic reading of prolonged QTc must be confirmed by manual reading. Prior to conclusion that an episode of prolongation of the QTc is due to study drug, thorough consideration should be given to potential precipitating factors (eg, change in patient clinical condition, effect of concurrent medication, electrolyte disturbance) and possible evaluation by a specialist. If QTc reverts to less than 500 msec, and in the judgment of investigator and sponsor is determined to be due to a cause other than study drug, treatment may be continued with regular ECG monitoring.

Prior to concluding that an episode of prolongation of the QTc interval is due to lorlatinib, thorough consideration should be given to potential precipitating factors (eg, change in patient clinical condition, effect of concurrent medication, electrolyte disturbance) and possible evaluation by specialist.

If a patient experiences PR interval prolongation >200 msec or second-degree or third-degree AV block, while on treatment with lorlatinib, refer to Section 5.5, Table 6.

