4.3.4. ECG Parameters

For analyses of ECG parameters, no values will be imputed for missing data. If one or two of the triplicate measurements for an ECG parameter are missing, the average of the remaining two measurements or the single measurement can be used in the analyses. If all triplicate measurements are missing at a time point for an ECG parameter, no values will be imputed for this time point and no analyses related to this time point will be performed.

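### SAP 5.5.4 assumes a triplicate ECG at every scheduled visit, but single tracings are scheduled from Cycle 3, so the maximum QTc and PR tables by hepatic group mix unlike readings and rise with time on treatment

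*SAP*

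**What the plan says.** **Replication.** SAP 5.5.4: "All patients require a triplicate ECG measurement at screening and at each scheduled time point during treatment". It then sets the analysis value: "ECG measurements (an average of the triplicate measurements) will be used for the statistical analysis and all data presentations". SAP 3.3 makes the baseline a triplicate average as well.

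**Schedule.** Footnote 14 of the protocol's Schedule of Activities differs. Triplicates are taken as follows: "Triplicate ECG will be performed at screening, times 0 (predose) 1, 2, 4, 10 and 24 hours post dose on Cycle 1 Day 1", the same times on Cycle 2 Day 1, and "predose on days 8 and 15 in cycle 1, and at the end of treatment". After that: "Single reading ECG will be collected pre-dose on Day 1 of Cycle 3 and every cycle thereafter". Protocol 7.1.6 also opens by calling for triplicates at all assessments, but it then refers on-treatment ECGs to the schedule and speaks of the time points that need triplicates.

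**Fallback.** Under SAP 4.3.4, if replicates are missing, "the average of the remaining two measurements or the single measurement can be used in the analyses".

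**Tables.** SAP 5.5.4 plans, for PR: "The number (%) of subjects with maximum post-dose PR interval values and maximum increases from baseline in the following categories will be tabulated". QTc has matching categories, with change bands of 30 to <60 and ≥60 msec, and PR has a shift from baseline to worst on study. None of these is limited to triplicates or to a shared period. Repeat ECGs done for safety enter the outlier analysis as individual values.

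**QTc source.** SAP 5.5.4 takes QTcF and QTcB from the sites on the CRF page that also carries QT and RR. Its category table says only QTc. Protocol 9.4.1 names Fridericia as the default correction.

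**The concern.** The two documents disagree on what a scheduled ECG is from Cycle 3 onward. SAP 4.3.4 lets the analysis run, but it was written for missed replicates. Applied to planned single tracings, it puts them beside triplicate means without comment.

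A patient's maximum grows with the number of readings and with the noise of each reading. Both depend on how long the patient stays on treatment, which is open-ended. Two hepatic groups with identical ECG behaviour but different treatment durations would therefore be expected to show different outlier rates. The effect of hepatic impairment on safety is a stated secondary objective, so readers will compare these columns.

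A second mixing starts at the same point. Group A2, the control for Group C, takes Group C's dose only until the Cycle 2 Day 1 PK assessment is complete and then goes to 100 mg QD, while Group C continues on its own dose (Protocol Table 4; SAP Table 2). SAP 5 splits groups by dose level, but does not say how a within-patient maximum handles A2's switch.

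**Working it through.** The documents give no ECG variance or outlier rate, so there is no planned figure to reproduce. The SDs below are assumptions, shown over a range.

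**Readings per patient (footnote 14).** Triplicates after baseline through Cycle 2 Day 1 + 24 h: 5 (Cycle 1 Day 1 post-dose) + 2 (Days 8 and 15) + 6 (Cycle 2 Day 1) = 13. Single tracings: one per cycle from Cycle 3, so 6 by Cycle 8 Day 1 and 12 by Cycle 14 Day 1.

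**Noise.** Let σo be the SD between occasions and σr the SD between replicates. A triplicate mean has variance sT² = σo² + σr²/3; a single tracing has sS² = σo² + σr². The replicate error of a single tracing is √3 = 1.73 times that of a triplicate mean. In the change from a triplicate baseline, the replicate part has variance (1/3 + 1/3)σr² for a triplicate and (1 + 1/3)σr² for a single tracing, which is double. At σr = 8 the SDs are 6.5 and 9.2 msec.

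**Chance of a maximum QTc increase ≥30 msec with no drug effect.** With baseline error b, independent occasions and m later single tracings:

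P = 1 − ∫ φ(b; 0, sT) · Φ((30+b)/sT)^13 · Φ((30+b)/sS)^m db

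Putting sT in place of sS gives the result had the later readings been triplicates.

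| σo / σr (msec) | No later reading | 6 singles | 6 triplicates | 12 singles | 12 triplicates |
|---|---|---|---|---|---|
| 6 / 8 | 2.4% | 5.9% | 3.2% | 8.7% | 3.9% |
| 8 / 8 | 8.5% | 14.1% | 10.8% | 18.4% | 12.7% |
| 10 / 8 | 17.8% | 24.9% | 21.7% | 30.1% | 24.8% |

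At 8/8 the rise after six singles is 14.1 − 8.5 = 5.6 points. Of this, 10.8 − 8.5 = 2.3 points (about 40%) come from visit count alone and 3.3 from single-tracing noise. At 6/8 the rise is 5.9 − 2.4 = 3.5 points, of which 3.2 − 2.4 = 0.8 is visit count. Counting the end-of-treatment triplicate as a 14th reading adds at most 0.4 points in the first two rows.

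**PR.** For a change ≥40 msec, SDs 10/8, 14 triplicates and no drug effect: 4.7% with no later reading and 9.9% after 12 singles (7.2% if triplicates). The late tracings are predose, whereas Protocol 1.2.1.2.1.6 reports PR prolongation as most notable at 1–2 hours post-dose. Assuming PR is up 15 msec at the triplicates and 8 msec at late predose visits, the figures are 30.8% and 35.9% (33.1% if triplicates). The proportional effect is much smaller.

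**QTc formula.** QTcF = QT/RR^(1/3) and QTcB = QT/RR^(1/2). QT 360 at 90 bpm (RR 0.667 s) gives 412.1 and 440.9, 28.8 apart. QT 340 at 100 bpm (RR 0.6 s) gives 403.1 and 438.9, 35.8 apart. Such a gap appears in the change only if the formula differs between baseline and a later reading; a consistent error largely cancels.

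**The case against.** **Worst-case summaries are meant to be inclusive.** Protocol 9.4.1 plans maxima across time points and includes unscheduled readings, and the SAP treats laboratory tests and vital signs in a similar way. Replacing these tables with a Cycle 1–2 version would remove late outliers from the main display, along with all of A2's exposure at 100 mg. This stands, and it is why the fix adds tables rather than replacing them. SAP 5.5.5 does show the same care elsewhere: its LVEF categories count only assessments made by the baseline method.

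**The effect is small.** The tables are descriptive, and values by nominal visit already show the shared triplicates. About 76 patients over five groups is roughly 15 each. At 8/8, 5.6 points is 15 × 0.056 = 0.8 of a patient, and only if one whole group had six late tracings and another had none. This also stands; it limits the weight of the point but does not remove the contradiction.

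**Stronger readings.** A reader might infer that normal-function controls stay on treatment longer, so that a true excess in impaired patients would be hidden. The documents say nothing on duration by group, so no direction can be claimed. A reader might also take Protocol 7.1.6 as a general warning about site QTc values. Its instruction on "verifying that the machine reading is accurate and that the Fridericia correction formula is applied" applies to QTc above 500 msec. Because QTcF and QTcB are collected separately with QT and RR, a swapped formula can be detected if someone recomputes it.

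**Conclusion.** The contradiction between SAP 5.5.4 and footnote 14 is plain. It follows from the text, not from the assumed SDs, that the maximum QTc and PR categories and the PR shift mix two kinds of reading and tend to rise with treatment duration. After Cycle 2 Day 1, the A2-versus-C comparison can also mix doses.

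The size is conditional. Over SDs of 6/8 to 8/8 msec, with independent occasions and no drug effect, six single tracings raise the chance of a maximum QTc increase of 30 msec or more by about 3.5 to 5.6 points. Roughly a quarter to two fifths of that would remain with triplicates. PR is less exposed. Neither the direction nor the actual size of any between-group bias can be known from the documents.

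The formula issue is a secondary safeguard; the documents give no sign that such an error is expected. This is a minor point, but an inexpensive one to settle before the tables are programmed.

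**What to change.** In SAP 5.5.4:

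1. Correct the triplicate sentence to match footnote 14: triplicate at screening, through Cycle 2 Day 1 + 24 h and at end of treatment; single predose tracing on Day 1 of Cycle 3 and later cycles.
2. Keep the full on-treatment worst-case tables, including unscheduled readings. Add the same maximum-value, maximum-change and PR shift tables restricted to scheduled triplicates through Cycle 2 Day 1 + 24 h, and name these as the basis for comparing hepatic groups. The window closes before A2's planned switch to 100 mg QD.
3. Derive QTcF (the protocol default) and QTcB by program from CRF QT and RR, state which correction the category table uses, and keep the site-entered values only as a query check.

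The cost is SAP wording, a short derivation and one extra set of descriptive tables. No reading is lost. One limit remains: patients who stop before Cycle 2 Day 1 still contribute fewer readings, so the restricted tables should state how many triplicate time points each group supplied.

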5.5.5. Left Ventricular Ejection Fraction

LVEF% will be summarized using simple descriptive statistics (mean, SD, median, Q1, Q3, minimum, and maximum) of actual values and changes from baseline for each nominal visit over time. In addition, LVEF% will be summarized as frequency (number and percentage) of patients with:

- a shift from baseline normal to at least one result below the institutional lower limit of normal during the on-treatment period;
- \geq 20-point decrease from baseline in LVEF%.

A patient will be included in the categories above if any post-baseline assessment (including unscheduled assessments) meet the criteria; however only post-baseline assessments which use the same method of assessment (ECHO or MUGA) as baseline will be considered.

5.5.6. Physical Examination

Individual patient data will be listed.

5.5.7. ECOG Performance Status

The ECOG shift from baseline to the highest score during the post-baseline period will be summarized by hepatic function group.

6. INTERIM ANALYSES

No formal interim analysis is planned. However, an interim PK and safety analysis will be done when 3 PK evaluable patients have been enrolled in group C1 to determine the dose regimen for groups C2 and D. Final analyses of PK and all other endpoints will follow the official database release at the end of the study. In case an early reporting of PK results is necessary, the study database will be released for final reporting of PK, safety and efficacy data after PK collection in all patients is completed. Then, a supplement report will be generated to only include additional safety and efficacy data after all patients completed the study.

8. APPENDICES

Appendix 1. Relative Dose

Overall exposure will be summarized as dose received relative to intended dose (relative dose [RD]).

Actual total dose in a cycle or overall is the sum of the actual doses of PF-06463922 received in a cycle or overall, respectively.

Relative dose [RD]: The basic intent is to evaluate dose per day factoring in dose reductions or interruptions.

Overall RD (%) = $100 \times$ [overall actual total dose] / [intended total dose per day × number of days from C1D1 to last dose of PF-06463922].

Note:

- The Intended total daily dose of PF-06463922 remains constant; the intended dose level is fixed at the start of treatment for each hepatic group;
- What is described above remains the same for the calculations even if the intended dose level changes, per protocol, during the study.

Appendix 2. SAS Code for Analyses

An example of the PROC MIXED code for PK parameter analysis is provided below:

proc mixed data=tab.pk; class group; model l&var=group/s cl alpha=0.1 ddfm=KR; lsmeans group; estimate 'Moderate vs Normal' group 0 -1 0 1 /cl alpha=0.1; estimate 'Mild vs Normal' group -1 0 1 0 /cl alpha=0.1; ods output lsmeans=lms; ods output solutionf=fixedcoef;

run;

/* Letter assignments for group within the estimate statement above are as follows;

Group A1 = Normal (Reference) Group B = Mild (Test) Group A2 = Normal (Reference) Group C = Moderate (Test)

Note: Group B (Test) will be compared to Group A1 (Reference) and Group C (Test) will be compared with Group A2 (Reference)

*/;
